7.5 Appetite scores using Visual Analog Scales (VAS)

Appetite scores will be used to assess the satiety power of the test (common bean) product among T2DM participants. The appetite score will be taken on one study day, that is, after consumption of the bean product. Subjective measures of appetite will be taken prior to, and at predetermined time intervals after consumption of the test meal. Appetite score refers to the average between hunger, desire to eat, prospective consumption and a 100-fullness score. The appetite score will be assessed at before and after consumption of test product at time points 0, 15, 30, 45, 60, 90 and 120 minutes. Participants will be given a short questionnaire to assess satiety.

A single vertical mark best expressing the participants' response will be made on an anchored 100 mm VAS scale. The anchor on the left and right will express the most positive and the most negative rating respectively (see Appendix 7). The response will be quantified by measuring the distance between the left anchor and the marking made. The questionnaires will be made as a small brochure booklet showing one question at a time [54][55]. Participants will be asked to remain silent while filling out their VAS. Between evaluations, they will be allowed to read or use their phones. The participants will not be allowed to discuss with each other or refer to previous ratings when filling out the VAS.

Blood draw + Appetite scores

Figure 3: Summary of protocol for the assessment of postprandial glycemic, insulinemic and satiety responses

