Appendix 3: VAS in assessment of appetite sensations

| | | |
|---------------------|---|-----------------------------|
| Not at all hungry | How hungry do you feel? | Extremely hungry |
| Not at all full | How full do you feel? | Extremely full |
| Not at all satiated | How satiated are you? | Extremely satiated |
| Not at all strong | How strong is your desire to eat? | Extremely strong |
| Nothing at all | How much could you eat right now? | A very large amount of food |
| Yes, very much | Would you like to eat something sweet? | No, not at all |
| Yes, very much | Would you like to eat something salty? | Yes, very much |
| Yes, very much | Would you like to eat something fatty? | Yes, very much |

Hunger: A compelling need or desire for food; the painful sensation or state of weakness caused by the need of food

Satiety: Fullness that persists after eating; length of time until next eating occasion

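### The anchor sentence in section 7.5 contradicts the VAS form in Appendix 3, so a booklet built to that sentence would reverse or distort the appetite score; separately, the salty and fatty items cannot be interpreted as printed

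*Combined protocol and SAP*

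**What the plan says.** Section 7.5 asks for one mark per item on an "anchored 100 mm VAS scale" and gives three rules:

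- Direction: "The anchor on the left and right will express the most positive and the most negative rating respectively". The word *positive* is not defined.
- Scoring: "The response will be quantified by measuring the distance between the left anchor and the marking made".
- Composite: "Appetite score refers to the average between hunger, desire to eat, prospective consumption and a 100-fullness score".

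The direction sentence sends the reader to Appendix 7, which contains the COVID-19 precautions. Section 8.1 names Appendix 3 as the tool for appetite scores, and Appendix 3 is the only VAS form in the document.

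Appendix 3 has eight items. The first five have the low end on the left: "Not at all hungry" for hunger, "Not at all full" for fullness, "Not at all satiated" for satiety, and equivalent low anchors for desire to eat and prospective consumption. The sweet item runs the other way, from a strong yes on the left to a no on the right. The salty item ("Would you like to eat something salty") and the fatty item show the same strong yes at both ends.

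Section 9.3 plans averages of the marks, with Cronbach's alpha as the validity check. It gives no anchor direction.

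**The concern.** The direction sentence and the form cannot both be followed, and the scoring rule depends on direction. Distance from the left end measures hunger only if the left end means no hunger, and subtracting fullness from 100 makes sense only if the left end of that item means no fullness. A team that prints the booklet from the section 7.5 text would apply the stated formula correctly and still get a wrong score.

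Appetite is one of the three responses in the general objective (section 4.1), and satiety is part of the hypothesis (section 6.1). The score is collected on one study day only, after the bean product, so there is no reference-food session against which a wrong direction would stand out. According to section 7.5 the booklet is still to be made.

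The salty and fatty items are a separate fault. A line with the same label at both ends does not tell the participant, or the analyst, what a mark near either end means.

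**Working it through.** The plan gives no numerical result, sample-size calculation or effect size for the appetite score, so there is no figure to reproduce. The check applies the section 7.5 formula under each anchor layout.

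**Formula (section 7.5).** With hunger h, desire d, prospective consumption p and fullness f, each in mm from the low end:

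S = (h + d + p + (100 - f)) / 4

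**Readings of *positive*, set against Appendix 3.**

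- Highest intensity on the left: all four score items in Appendix 3 run the other way.
- Least appetite on the left: hunger, desire and prospective consumption agree with Appendix 3, but fullness (and the separate satiety item) does not.

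Neither natural reading fits the form. Greatest appetite on the left does not fit either: fullness would agree and the other three would not.

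**Effect of the first reading.** Every recorded item becomes 100 minus its true value:

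((100 - h) + (100 - d) + (100 - p) + (100 - (100 - f))) / 4 = 100 - S

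This holds for any ratings. A true fall from 70 to 30 is recorded as a rise from 30 to 70.

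**Effect of the second reading.** Only fullness flips, so the recorded score is S' = (h + d + p + f) / 4. A rise in fullness now works against the falls in the other three items.

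**Illustration.** The ratings are assumed, not taken from the document: fasting h = 70, d = 65, p = 60, f = 20; after the meal h = 20, d = 25, p = 30, f = 80.

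| Layout | Fasting | After meal | Change |
|---|---|---|---|
| Appendix 3 as printed | (70 + 65 + 60 + 80)/4 = 68.75 | (20 + 25 + 30 + 20)/4 = 23.75 | -45 |
| Section 7.5, highest intensity left | 100 - 68.75 = 31.25 | 100 - 23.75 = 76.25 | +45 |
| Section 7.5, least appetite left | (70 + 65 + 60 + 20)/4 = 53.75 | (20 + 25 + 30 + 80)/4 = 38.75 | -15 |

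For other ratings, the recorded change under the second reading equals the true change plus half the rise in fullness: here -45 + 60/2 = -15.

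**Would Cronbach's alpha notice?** Assume four items with equal variances and a common correlation r.

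- Correct layout: alpha = 4r / (1 + 3r). At r = 0.7 this is 2.8 / 3.1 = 0.903.
- All items reversed: every correlation keeps its sign, so alpha is unchanged (0.903 at r = 0.7).
- Only fullness flipped: the six pairwise correlations are three at +r and three at -r. They sum to zero, so alpha = (4/3)(1 - 4/4) = 0 for any r.

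**Salty and fatty items.** Neither is in the formula, so their weight in S is 0 under every layout. Their faulty anchors affect only those two items, and any average of all marks that might be taken under section 9.3.

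**The case against.** The best defence is that Appendix 3 is the working form. Section 8.1 names it as the tool, the contents list gives it as the VAS form, and Appendix 7 is so plainly unrelated that the wrong number would mislead few people. Used as printed and measured from the left, Appendix 3 orients all four score items correctly. Reversal therefore requires someone to set the form aside and build another from one sentence. Even then, full reversal is exactly 100 - S, and because the anchors are printed on the booklets the score could be restored without loss of data.

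Most of this stands, and it makes the harm conditional. It does not remove the contradiction: no sentence says which layout prevails, and the sentence that gives the direction is the one with the wrong reference.

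A reader might go further in three ways that the document does not support:

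- **That the appetite score is unreadable because two of eight items have no usable scale.** Those two items are not in the score; 0 of its 4 components are affected.
- **That the planned alpha check would miss any anchor error.** It misses only full reversal. With fullness alone flipped it would probably raise an alarm.
- **That the sweet item is also unusable.** Its two ends differ and are labelled, so it can be read as printed. Its opposite direction matters only if it is pooled with other items.

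**Conclusion.** The plan is wrong as written on two limited points.

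First, the section 7.5 direction sentence contradicts Appendix 3 and cites the wrong appendix. A booklet built to that sentence gives exactly 100 - S if *positive* means highest intensity, and alpha does not detect it. If *positive* means least appetite, the score is distorted: the change falls to one third of its true size in the example, and alpha would probably reveal it. The identity 100 - S needs no assumption. The one-third figure depends on the assumed ratings, and the alpha values on equal variances and a common correlation. It cannot be inferred that the score will in fact be reversed, since Appendix 3 used as printed gives the right direction.

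Second, the salty and fatty items cannot be interpreted with identical anchors. Marks made on those lines could not be rescued later. The sweet row prints a proper opposite anchor, which suggests a slip in the form, but the master copy should be checked.

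This should be corrected before data collection; it does not call the design into question.

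**What to change.** 1. In section 7.5, replace the direction sentence for the appetite-score items with: *left anchor = not at all / nothing at all (0 mm); right anchor = extremely / a very large amount (100 mm), as in Appendix 3*.
2. Change the section 7.5 cross-reference from Appendix 7 to Appendix 3.
3. In Appendix 3, give the salty and fatty items opposite anchors that match the sweet item (strong yes on the left, no on the right), and state that direction in the scoring rule.
4. State that the sweet, salty and fatty items are reported separately and do not enter the appetite score.

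The cost is a few lines of text, two corrected anchors and a check of the booklet before it is printed (a reprint if copies already exist). There is no effect on sample size, visits or analysis method.

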8. DATA COLLECTION

8.1 Data collection processes

Glycemic index and glycemic response (*Appendix 2*)

- a. Equi-carbohydrate (50g or 25g) portions of the common bean product
- b. 24-hour of dietary recall
- c. Anthropometry: weight, height, waist & hip circumference
- d. Body composition: BIA
- e. Biochemical samples: Blood

Food insulin index (FII) and insulin response (*Appendix 2*)

- a. Iso-caloric (240kJ) portions of the common bean product
- b. 24-hour of dietary recall
- c. Anthropometry: weight, height, waist & hip circumference
- d. Body composition: BIA
- e. Biochemical samples: Blood

Appetite scores (*Appendix 3*)

- a. Visual analog scales
- b. Timers

BIA will be assessed with the Bodystat 500 (Bodystat, UK). Raw data on impedance, resistance, reactance and phase angle will be added to already validated equations to calculate fat free mass, body fat and hydration [56].

For blood draw, handling and processing; phlebotomists from the Kenya Medical and Research Institute (KEMRI) will be engaged. A catheter will be placed in the cubital vein. Blood samples will be collected at seven time-points; 0, 15, 30, 45, 60, 90 and 120 minutes. For each bleeding moment ~2 ml of blood will be drawn from the participant. Plain tubes will be used for blood collection. After collection, whole-blood samples will be labelled with codes with participant

codes and separated based on time-collection point. A drop of blood will then be obtained for determination of haemoglobin concentration using the Hemocue 301 portable device. The tubes will then be placed immediately into insulated coolers containing ice/cold packs at around 4°C awaiting centrifuging. Centrifuging will be within 30 minutes of sample collection. After centrifuging, serum will be separated and divided in aliquots. Cryovials containing the aliquots will be labelled (with participant code and test to be run), wrapped with aluminum foil (to reduce chances of light degradation) and secured together with rubber bands. They will then be put in a portable freezer. At the end of sample collection and separation, the aliquots will be dropped into a liquid nitrogen tank awaiting transportation to analytical laboratories (LANCET), for further analysis. Necessary precautions will be taken to ensure a dust and light free environment during the blood sample collection and handling.

Single use for alcohol swabs, clean disposable latex-free gloves, disposable needles, catheters and plain tubes will be observed. Biological waste and sharps will be disposed appropriately in biological hazard bags and biohazard box respectively and later on disposed of together with the hospital waste at the participating hospital facilities in Makueni County and JKUAT hospitals.

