Insulin release can be triggered by other food components such as proteins and fats. The food insulin index (FII) allows for testing of foods with no or low carbohydrate content. It shows the observed (plasma) insulinemic response to consumption of a particular food compared to an isocaloric portion of the reference food over a 2 hour period. It is obtained as: $\frac{\text{iAUC for 1000kJ test food}}{\text{iAUC for 1000kJ reference food}} * 100$. FII has previously been reported to have potential of reducing postprandial hyperinsulinaemia in T2DM management [47].

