7. STUDY DESIGN AND SAMPLING STRATEGY

7.1 Glyceimic index (GI) and glyceimic response study

The GI evaluates the blood-raising ability of equi-carbohydrate portions of different single foods or mixed meals. To assess the GI of the common bean product *in vivo*, 10 healthy volunteers will be recruited. The selection of the number of participants, and the inclusion and exclusion criteria is based on the ISO_26642_2010 standard [53].

The 10 healthy volunteers will be recruited from Jomo Kenyatta University of Agriculture and Technology (JKUAT) and handled at the JKUAT University Hospital.

Inclusion criteria:

- Male or female 18-69 years
- No known food allergies or intolerances
- No prescription medication² (excluding oral contraceptives) known to affect glucose intolerance (e.g. steroids, protease inhibitors, antipsychotics e.t.c.)

Exclusion criteria

- Known history of diabetes mellitus or use of anti-hyperglycaemic medication or insulin
- Alcohol or tobacco use in the evening preceding the test
- Vigorous exercise on the morning of the test
- Undergone major medical/surgical event needing hospitalization within the preceding 3 months
- Presence of disease or drug influencing digestion and absorption of medicine

Glycemic response associated with consumption of the common bean product will be assessed in 10 T2DM patients in Makueni County. The participants will be recruited from the **Makueni Level-5 and Mbooni sub-county hospitals** which run a diabetes outpatient clinic.

Inclusion criteria:

- Male or female aged 18-69 years
- Previously diagnosed with type 2 diabetes
- Consenting to participate

Exclusion criteria:

- Use of prescription medication
- History of eating disorders and irregular eating habits
- Use of tobacco or alcohol
- Females experiencing menstrual period or adverse premenstrual symptoms

For the reference food, we will use either anhydrous glucose powder, 50g or dextrose (glucose monohydrate), 55g. The reference food will be dissolved in 250ml of water and refrigerated for use within 72 hours after preparation. Participants will be fed with an equi-carbohydrate portion of the common bean product to the reference food.

² Stable doses of oral contraceptives, acetylsalicylic acid, thyroxin, vitamins and mineral supplements or drugs to treat hypertension or osteoporosis are acceptable

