7.2 Food insulin index (FII) and insulin response

To assess the FII of the common bean product *in vivo*, 10 healthy volunteers will be recruited from Jomo Kenyatta University of Agriculture and Technology. Insulin response associated with consumption of the common bean product will be assessed in 10 T2DM patients in Makueni County. Participants will be fed with iso-caloric (240 kilocalorie) portions of the test food and reference food.

Inclusion and exclusion criteria for the FII and insulin response used will be as cited in GI study (see section 7.1).

The FII of the food will be measured over a 120 min period starting at the ingestion of the common bean product. The test food and reference food will be assessed in each subject on separate days with a 1 week period between each study day.

The FII value of the common bean product will be calculated as follows: = [iAUC of the common bean product/individual subject's average iAUC of reference food]*100. The overall FII will then be obtained as: The mean FII value for the 10 participants.

³ The standard was issued under licence to [name] (co-principal investigator)

Insulin response associated with consumption of the common bean product will be assessed in 10 T2DM patients in Makueni County.

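### The food insulin index (FII) portion is 240 kcal in section 7.2 but 240 kJ in section 8.1, a 4.18-fold conflict, and section 7.2 does not say whether the glucose reference applies or in what amount

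*Combined protocol and SAP*

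**What the plan says.** Section 3.5 defines the FII as the insulin response to a food "compared to an isocaloric portion of the reference food over a 2 hour period". The numerator is "iAUC for 1000kJ test food" and the denominator "iAUC for 1000kJ reference food".

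Section 7.2, the design section for the FII, says: "Participants will be fed with iso-caloric (240 kilocalorie) portions of the test food and reference food". Section 8.1, which lists what is needed for data collection in the same test, says: "Iso-caloric (240kJ) portions of the common bean product". That list gives no energy for the reference.

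On the analysis, section 7.2 states "The FII value of the common bean product will be calculated as follows". The formula that follows is the bean product's incremental area under the curve (iAUC), divided by the same subject's average reference iAUC, times 100.

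On the reference food, section 7.1 (the glycemic index, GI, study) says: "For the reference food, we will use either anhydrous glucose powder, 50g or dextrose (glucose monohydrate), 55g". The GI paragraph of section 3.5 names the same two options. The only link from section 7.2 back to section 7.1 concerns eligibility: "Inclusion and exclusion criteria for the FII and insulin response used will be as cited in GI study (see section 7.1". Section 7.4 describes one procedure for GI and FII and speaks of a reference food without saying which food or portion applies to which index.

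**The concern.** The FII is meaningful only if the two foods are given at equal energy. The formula has no energy term, so any mismatch in portions goes straight into the index and cannot be separated afterwards from a true difference in insulin response. Two instructions for the same meal that differ more than fourfold therefore bear directly on the estimate. The conflict also sits where it can do harm, because section 8.1 is the kind of list from which staff prepare portions.

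The reference side has a related gap. The GI test matches foods on carbohydrate and the FII matches them on energy. A reference amount written for the first does not automatically suit the second.

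**Working it through.** **Inputs.** 240 kcal for both foods (section 7.2); 240 kJ for the bean product (section 8.1); 1000 kJ for both foods (section 3.5); 50 g anhydrous glucose or 55 g dextrose (section 7.1); assay and lunch counts (section 12.3). Assumed, because the documents do not give them: 1 kcal = 4.184 kJ, and 3.75 to 4 kcal per gram of glucose.

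**1. Section 7.2 against the definition.** 240 × 4.184 = 1,004.2 kJ, and 1,004.2 / 1,000 = 1.004. Conversion factors from 4.18 to 4.2 give 1,003 to 1,008 kJ. Sections 7.2 and 3.5 therefore agree.

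**2. Section 8.1 against both.** 240 / 4.184 = 57.4 kcal. Against the definition, 240 / 1,000 = 24%. Against section 7.2, 1,004.2 / 240 = 4.18.

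**3. What each reading would do.**

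| Reading | Bean product | Reference | Iso-caloric? | Against 1000 kJ |
|---|---|---|---|---|
| Section 7.2 for both | 1,004 kJ | 1,004 kJ | yes | 100.4% |
| Section 8.1 figure for both | 240 kJ | 240 kJ | yes | 24% |
| Section 8.1 for bean, 7.2 for reference | 240 kJ | 1,004 kJ | no (240 / 1,004.2 = 23.9%) | 24% and 100.4% |

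**4. The stated glucose amounts.** 50 g × 3.75 = 187.5 kcal and 50 g × 4 = 200 kcal. For dextrose as the monohydrate, 55 g × 180.16 / 198.17 = 50.0 g of glucose, so the energy is the same.

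- Against 240 kcal: 1 − 200/240 = 17% and 1 − 187.5/240 = 22% short.
- Against 240 kJ: 187.5 / 57.4 = 3.3 and 200 / 57.4 = 3.5 times too much.
- A wider assumption of 15.6 to 17.0 kJ/g gives 780 to 850 kJ (186 to 203 kcal), with the same conclusion.
- The 25 g carbohydrate option in sections 3.5 and 8.1 would give 25 × 3.75 to 25 × 4, or 94 to 100 kcal, which also matches neither.

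**5. Could GI and FII share sessions?** The budget has 30 fasting and 180 later glucose assays, the same numbers for insulin, and 30 lunches. With seven samples per session (section 8.1), 210 / 7 = 30 sessions. Separate GI and FII testing with one reference and one test day each would need 10 × 2 × 2 = 40 sessions in the healthy volunteers alone. The counts suggest shared sessions, but the plan does not say so.

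**The case against.** The strongest reply is that this is one discrepant unit in a checklist. The design section and the definition agree to within 0.5%, so an attentive reader would notice the odd figure. That is fair as to how easily it can be found. It does not remove the contradiction, which redaction or text extraction does not explain: one section spells out kilocalorie and the other prints kJ.

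Two stronger readings are tempting, and the documents do not support them.

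- **That the FII would be grossly biased.** A reader might pair the 240 kJ bean portion with a 240 kcal reference. The FII would then read about 76% too low if insulin iAUC were proportional to energy (1 − 0.239), or about 51% too low if it followed the square root (1 − √0.239 = 1 − 0.489). But section 7.2 sets both foods in one sentence, and section 8.1 itself calls the portions iso-caloric. It lists only the bean product because it is a checklist; its GI entry does the same. The two response models have no basis in the documents. These figures describe a worst-case mixed reading only, not an expected error.
- **That the FII has no named reference food.** Sections 3.5 (GI paragraph) and 7.1 name glucose or dextrose, and the FII text in section 3.5 and the joint procedure in section 7.4 keep the same term. One reference food throughout is the natural reading. What remains is narrower: section 7.2 does not confirm it, and no stated amount fits either FII energy.

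It is also fair that fixing a portion by energy is not a defect in itself, since a mass follows once food and energy are settled. No section assigns 50 g or 55 g to the FII, so step 4 shows a gap and not a second contradiction.

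**Conclusion.** The concern holds. The FII portion is stated at two energies that differ by a factor of 4.18, and the smaller is 24% of the energy in the plan's own definition. This rests only on unit conversion. It is a unit inconsistency and not a faulty calculation in the plan. Its consequence depends on what is actually served: equal portions at either energy keep the ratio iso-caloric, while mixed portions do not, and the analysis cannot repair that.

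The secondary point also holds, in limited form. The plan does not confirm that the glucose reference carries over to the FII, and the stated amount supplies about 188 to 200 kcal under the assumed energy factors. This matters more if GI and FII share sessions, because one bean portion and one reference portion would then have to match on carbohydrate and on energy together. That last step is an inference from the budget counts.

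Which energy is intended is for the protocol team to say.

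**What to change.** 1. Reconcile sections 3.5, 7.2 and 8.1 to one energy figure in one unit, stated for both the bean product and the reference.
2. State in section 7.2 whether the glucose or dextrose reference of section 7.1 is also the FII reference, and what amount of it supplies that same energy.
3. State whether GI and FII are measured in the same sessions. If they are, say how the equal-carbohydrate and equal-energy conditions are both met.

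Items 1 and 2 are wording: one unit and one sentence. Item 3 is also wording if the existing sessions already meet both conditions. If separate FII portions turn out to be needed beyond the 30 sessions that the budget appears to cover, there is a real cost. At the budgeted prices, the insulin assays for one extra session come to 3,849 + 6 × 4,149 = KSh 28,743, or KSh 287,430 for ten. All of this should be settled before the first meal is prepared.
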